13.5 Followup of adverse events and serious adverse events

All AEs and all SAEs must be followed by the investigator until resolution, or until in the opinion of the investigator, the AE has stabilised or is recognised as permanent, or until the subject is lost to follow up, whichever comes first. Followup investigations may be necessary according to the investigator's medical judgement.

14. Statistical analysis

14.1 General considerations

The statistical analysis principles described below will be supplemented by a comprehensive statistical analysis plan (SAP) which will be finalised before the database is locked. This will contain details of methods for handling missing data, early withdrawals, data derivations and presentation. Any changes to the statistical analysis plan will be described and justified in the final report.

The descriptive summary for the categorical variables will include counts and percentages. The descriptive summary for the continuous variables will include number of subjects (n), means, medians, standard deviations, and minimum and maximum values. All data will be listed for all subjects. Treatment period order will be ignored in any treatment comparisons. Results will be presented in a descriptive format by treatment within each treatment period and overall. Treatment comparisons will take into account the paired nature of the treatment responses where feasible. As this is a Phase IIa proof of concept study, no formal statistical hypotheses are being specified although some may be investigated as part of the data presentation, in which case corresponding 95% confidence intervals will be presented and p-values of <0.05 will be declared statistically significant.

14.2 Sample size

No formal statistical sample size estimation has been performed due to the exploratory nature of this study. Rather the sample size is based on clinical and practical considerations.

14.3 Analysis populations

14.3.1 Full analysis set

The Full analysis set (FAS) consists of all subjects enrolled and randomised into the study. The FAS population will be used for summaries of subject disposition, demographic and baseline characteristics. Subjects will be analysed according to the treatment group they were assigned at randomisation.

14.3.2 Per protocol population

A per-protocol (PP) population will be used for efficacy analyses and to analyse exploratory endpoints. The PP population will be based on IMP exposure, including the time of any episodes of vomiting and major protocol deviations.

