The safety population includes all subjects who receive at least one dose of IMP and will be the population used for the analysis of safety endpoints. The full analysis set (FAS) population will be used to present demographic and other baseline characteristics and summaries of efficacy endpoints. A per-protocol (PP) population will be used as the primary population for efficacy analyses and to analyse exploratory endpoints. The PP population will be based on IMP exposure, including the time of any episodes of vomiting and major protocol deviations.

The descriptive summaries for the categorical variables will include counts and percentages. The descriptive summaries for the continuous variables will include number of subjects (n), means, medians, standard deviations, and minimum and maximum values. All data will be listed for all subjects. As this is a Phase IIa proof of concept study, no formal statistical hypotheses are being specified although some may be investigated as part of the data presentation. A p-value of <0.05 will be declared statistically significant. Treatment period order will be ignored in any treatment comparisons. Results will be presented in a descriptive format by treatment within each treatment period and overall. Treatment comparisons will take into account the paired nature of the treatment responses where feasible.

Individual pain score-time profiles for each treatment within each subject will be presented graphically. The difference between the NRS pain scores at each

timepoint for LAT8881 60 mg compared with placebo within each subject will be estimated and presented graphically. The number of subjects, mean, standard deviation, minimum and maximum NRS pain score at each timepoint, change from baseline, difference between treatments at each timepoint and change from baseline difference between treatments will be presented for each treatment overall and within each treatment period.

Nausea, photophobia and phonophobia symptom scores will be summarised and presented in the same way as the pain scores. The number and percent of headaches with each most troublesome symptom of migraine including nausea, cognitive impairment, dizziness, functional disability, photophobia phonophobia and vomiting will be summarised for each treatment. The most troublesome symptom scores will be summarised and presented in the same way as the pain scores.

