3.2.2 Clinical studies

Six clinical studies with LAT8881 have been completed, with over 700 subjects treated with LAT8881 ([REDACTED]). These studies were designed to investigate the safety and tolerability of LAT8881 and subsequently its efficacy in the treatment of obesity [REDACTED].

A seventh study (LAT-NP-001) to investigate the safety and efficacy of LAT8881 in neuropathic pain at a dose of 60 mg per day (30 mg twice daily) has recently commenced and is recruiting subjects. No results from this study are yet available.

[REDACTED]

[REDACTED]	[REDACTED]	[REDACTED]	[REDACTED]	[REDACTED]	[REDACTED]
[REDACTED]	[REDACTED]	[REDACTED]	[REDACTED]	[REDACTED]	[REDACTED]
[REDACTED]	[REDACTED]	[REDACTED]	[REDACTED]	[REDACTED]	[REDACTED]
[REDACTED]	[REDACTED]	[REDACTED]	[REDACTED]	[REDACTED]	[REDACTED]
[REDACTED]	[REDACTED]	[REDACTED]	[REDACTED]	[REDACTED]	[REDACTED]
[REDACTED]	[REDACTED]	[REDACTED]	[REDACTED]	[REDACTED]	[REDACTED]
[REDACTED]	[REDACTED]	[REDACTED]	[REDACTED]	[REDACTED]	[REDACTED]
[REDACTED]	[REDACTED]	[REDACTED]	[REDACTED]	[REDACTED]	[REDACTED]

In all development studies for obesity, it was noted that the study drug was well tolerated. The only dose-related adverse event (AE) trend was an increased incidence of gastrointestinal effects and general body symptoms of abdominal pain and headache in Study METAOD004 at 54 mg. This trend was not observed in subsequent studies.

More detailed results from these clinical studies with LAT8881 are available in the Investigator's Brochure.

4. Study objectives

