6.2 Exclusion criteria

Subjects who meet any of the following criteria will be excluded from the study:

1. Unable to distinguish migraine from other primary headache conditions
2. Average of 15 or more headache (migraine or nonmigraine) days per month or history of more than 25% of headaches occurring at time of wakening (wake up headaches)
3. History of aura lasting more than 60 minutes
4. History of vomiting within 2 hours of onset of a migraine headache in more than 25% of migraine headaches
5. Medication overuse headache, defined as:
 - a. use of opioids, triptans or ergot alkaloids or any combination of these medications for treatment of headaches 10 or more days per month during the 90 days prior to screening OR
 - b. Non-steroidal anti-inflammatory drugs (NSAIDs) or simple analgesics for treatment of headaches on more than 14 days per month during the 90 days prior to screening
6. Recent (3 years) history of frequent or chronic hemiplegic/ basilar migraine, tension headache, retinal migraine, ophthalmoplegic migraine as per ICHD classification, or treatment resistant atypical migraine

7. Hospital admission for status migrainosis or medication overuse headache within 6 months of screening
8. Current clinically significant systemic disease or neurological or psychiatric condition which in the opinion of the investigator or sponsor could jeopardise the safety of the subject or the validity of the study results
9. Cerebrovascular disease, including but not limited to a history of stroke or recent (3 years) transient ischaemic attack (TIA)
10. Major surgery within 6 weeks of screening or planned during the study period
11. Clinically significant abnormality as assessed by the investigator or sponsor's medical monitor on haematology, biochemistry, vital signs, physical examination or 12-lead electrocardiogram (ECG)
12. Malignancy within 5 years of screening, with the exception of carcinoma *in situ*, non-melanoma skin cancers and prostate cancer not requiring treatment or on stable (> 6 months) treatment with hormone therapy
13. History of alcohol abuse, illicit or illegal drug use in the last 2 years
14. Use of Prohibited medications or treatments within the specified time period before Screening or planned during the study
15. Participation in another clinical trial or administration of any investigational product or experimental product within 60 days or 5 half-lives (whichever is longer)

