11.5.2 Migraine symptoms

Each subject will specify his/her most troublesome symptom at baseline (Day 1).

On the day of a migraine headache, baseline information about the headache should be recorded to verify that the headache was an acute migraine headache including headache intensity, aura, presence or absence of associated symptoms, unilaterality or bilaterality of the headache, aggravation by exercise, throbbing or nonthrobbing.

The subject's symptoms will be recorded on an 11-point Likert scale. This scale allows the subject to record the presence of the symptom from 0 = no symptoms to 10 being severe symptoms. Symptom assessments will be recorded in the subject's diary prior to dosing (t = 0 min) and at 0.5, 1, 1.5, 2, 4, 8 and 24 hours post dose. Symptoms to be recorded include nausea, photophobia and phonophobia plus the subject's most troublesome symptom (eg cognitive impairment, dizziness and functional disability) if other than nausea, photophobia or phonophobia. Episodes of vomiting will also be recorded.

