14.5 Analysis of efficacy data

The primary population for analysis of efficacy data is the PP population. All summary tables and results of statistical analyses will be presented for the PP population for all efficacy endpoints. In addition, all

summary tables and results will be presented for the FAS population.

Individual pain score-time profiles for each treatment within each subject will be presented graphically. The difference between the NRS pain scores at each timepoint for LAT8881 60 mg compared with placebo within each subject will be estimated and presented graphically. The number of subjects, mean, standard deviation, minimum and maximum NRS pain score at each timepoint, change from baseline, difference between treatments at each timepoint and change from baseline difference between treatments will be presented for each treatment overall and within each treatment period.

Nausea, photophobia and phonophobia symptom scores will be summarised and presented in the same way as the pain scores. The number and percent of headaches with each most troublesome symptom of migraine including nausea, cognitive impairment, dizziness, functional disability, photophobia and phonophobia will be summarised for each treatment. The most troublesome symptom scores will be summarised and presented in the same way as the pain scores.

The number and percent of subjects with 'no headache pain' at each time point will be presented for each treatment. Two-way tables will present the presence/absence of pain classified for each treatment at each timepoint. Absence of pain will be defined as a pain NRS score of 0 or 1.

The number and percent of subjects who are "sustained pain-free" at 24 hours after dose of IMP will be presented by treatment. A two-way table will present the "sustained pain-free" status for subjects on each treatment.

The number and percent of subjects will be summarised by their first pain-free timepoint. A two-way table will present the classification of each subject's first pain-free timepoint by treatment. Kaplan-Meier curves will present the time to first pain-free timepoint.

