## 9.2 Per Protocol (PP) Population

The Per Protocol (PP) population will include all subjects who received at least one dose of IMP and excludes subjects who have any major protocol deviation impacting the study endpoints. Deviations

for exclusion from the PP population due to inadequate exposure to IMP or completeness of primary efficacy endpoint will be determined during the blinded review meeting prior to database lock.

*A per-protocol (PP) population will be used for efficacy analyses and to analyse exploratory endpoints.*

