#### 11.8.2.6 Migraine and Headache Diary

Migraine and headache diary details will be listed by subject. Menstrual cycle details will also be listed by subject.

In DDP: Listing 16.2.6.1, Listing 16.2.6.2 and Listing 16.2.6.5

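### The time of post-dose vomiting can decide who is in the primary efficacy population, with no fixed rule, no guaranteed analysis of all dosed attacks and no planned comparison of diary-recorded vomiting

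*Protocol*

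**What the plan says.** **Population.** Protocol 14.3.2 defines the PP set by exposure and deviations: "The PP population will be based on IMP exposure, including the time of any episodes of vomiting and major protocol deviations". The synopsis repeats this. Protocol 14.5 adds: "The primary population for analysis of efficacy data is the PP population". SAP 9.2 includes subjects with at least one dose and no major deviation affecting the endpoints. It does not mention vomiting, but it treats other deviations in these terms: "for exclusion from the PP population due to inadequate exposure to IMP or completeness of primary efficacy endpoint will be determined during the blinded review". SAP 11.8.1.3 fits the MMRM for pain to the PP population.

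**FAS.** Protocol 14.5 says that all efficacy summary tables and results will also be shown for the FAS. SAP 11.8 leaves FAS presentation to the blind review meeting, limits it to descriptive summaries, and ties it to how far the two populations differ in size.

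**Vomiting data.** Protocol 11.1.1 gives vomiting as an example of an associated symptom of migraine. Protocol 11.5.2 says of the attack diary: "Episodes of vomiting will also be recorded". SAP 11.8.2.6 says: "Migraine and headache diary details will be listed by subject". The symptom summaries in SAP 11.8.2.1 cover nausea, photophobia and phonophobia. The synopsis includes vomiting among the most-troublesome-symptom categories to be summarised by treatment; the matching sentence in Protocol 14.5 omits it.

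**Entry and earlier safety data.** Exclusion criterion 4 in Protocol 6.2 removes subjects with a "History of vomiting within 2 hours of onset of a migraine headache in more than 25% of migraine headaches", so subjects at or below that share may enter. Protocol 3.2.2 reports: "The only dose-related adverse event (AE) trend was an increased incidence of gastrointestinal effects", together with abdominal pain and headache, at 54 mg in one study. It adds that later studies did not show the trend.

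**The concern.** Whether and when a subject vomits after dosing is settled after randomisation and is part of how the attack unfolds. A drug that relieves the attack could reduce vomiting; a drug that upsets the gut could increase it. If such attacks leave the primary population at different rates on the two treatments, the attacks that remain are no longer comparable, even if those deciding do not know the allocation. Blinding prevents deliberate selection. It does not prevent selection by an event that itself depends on treatment.

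The direction could go either way. If vomiting attacks are worse on pain and more frequent on placebo, dropping them understates the drug effect. If they are more frequent on LAT8881, dropping them flatters the drug. SAP 9.2 speaks of excluding subjects, so a single episode might also cost both periods of a crossover pair.

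**Working it through.** **1. The plan's own figure.** Inflating 20 completers for 20% non-completion gives 20 / (1 − 0.20) = 25, against the 26 stated in Protocol 5.4. The point does not depend on this figure; the base used below is 20 completers × 2 attacks = 40.

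**2. What is fixed and what is open.**

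| Question | Protocol | SAP |
|---|---|---|
| Can vomiting affect PP membership? | Yes, through its timing (synopsis, 14.3.2) | Not named; possible through inadequate exposure (9.2) |
| Time window | None | None |
| Attack or subject dropped | Not stated | Worded at subject level (9.2) |
| Efficacy results on FAS | All tables and results (14.5) | Descriptive, decided at blind review (11.8) |
| Model on a set not filtered by vomiting | Not specified | None; MMRM on PP only (11.8.1.3) |
| Diary vomiting by treatment | Synopsis only, as a most-troublesome-symptom category | Listing only (11.8.2.6) |

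**3. Attacks at risk.** The documents give no expected vomiting rate, so v, the share of attacks with vomiting, is assumed at 5%, 10% and 25%. The last is the entry ceiling. Attacks affected = 40v. Subjects with vomiting in at least one of two attacks = 20 × [1 − (1 − v)²], treating attacks as independent.

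| v | Attacks of 40 | Subjects of 20 | Complete pairs left if any vomiting removes the subject |
|---|---|---|---|
| 5% | 2 | 1.95 | 18.05 |
| 10% | 4 | 3.8 | 16.2 |
| 25% | 10 | 8.75 | 11.25 |

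**4. Selection bias with no true effect on pain.** Assume that the liability to vomit has correlation ρ with change in pain (SD = s), and that every vomiting attack is dropped. The mean change among the remaining attacks then shifts by −ρ·s·φ(z)/(1 − v), with z = Φ⁻¹(1 − v). The factor φ(z)/(1 − v) is 0.195 at 10%, 0.350 at 20% and 0.424 at 25%. The bias, drug minus placebo, is −ρ·s times the difference in factors. The assumed ranges are ρ = 0.2 to 0.5 and s = 2.5 to 3.0 NRS points, so ρ·s runs from 0.5 to 1.5.

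- 20% on drug, 10% on placebo: 0.155 × 0.5 to 0.155 × 1.5, a bias of −0.08 to −0.23 points (favours drug).
- 25% on drug, 10% on placebo: 0.229 × 0.5 to 0.229 × 1.5, a bias of −0.11 to −0.34 points.
- 10% on drug, 25% on placebo: +0.11 to +0.34 points (against drug).
- Equal rates: 0.

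A simpler calculation agrees. If vomiting occurs in 15% of attacks on one treatment and 5% on the other, and those attacks improve by 2 points less, dropping them shifts the difference by (0.15 − 0.05) × 2 = 0.2 points. All these inputs are assumptions.

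**The case against.** The strongest reply is that an exposure-based primary population is a legitimate choice in a proof-of-concept study with no formal hypotheses: it asks what the drug does when it is absorbed. That stands. Moving to all dosed attacks as primary changes the question and is partly a matter of preference. It does not answer the missing rule or the lack of any guaranteed model on the unfiltered attacks.

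The bias is also small against the noise. With 20 pairs and an assumed SD of within-subject differences of 3 to 4 points, the standard error is 3/√20 to 4/√20, about 0.7 to 0.9. That limits the size of the point. The calculation further assumes that every vomiting attack is dropped whatever its timing, and that these attacks are worse on pain; the documents give no figure for either.

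Four stronger readings are tempting and are not supported.

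- *Vomiting is never compared between treatments.* The synopsis has it as a most-troublesome-symptom category by treatment, and vomiting reported as an AE would enter the by-treatment tables of SAP 11.9.1.2. Neither measures the incidence of diary vomiting. The most troublesome symptom is specified at baseline (Protocol 11.5.2), and Protocol 13.1.1 says that anticipated fluctuations of the disease need not be AEs.
- *Vomiting automatically excludes.* Protocol 14.3.2 makes its timing relevant to exposure. SAP 9.2 makes exclusion possible, not certain.
- *LAT8881 is known to cause vomiting.* The trend at 54 mg came from one study, was not seen later, and vomiting is not named. Protocol 5.2 also states that no notable AEs would reveal the treatment.
- *About 13 of 52 attacks are at stake.* That needs all 26 subjects to dose twice and all to sit at the 25% ceiling. The ceiling is counted from headache onset, and dosing may follow up to an hour later, so some of that vomiting would precede the dose.

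**Conclusion.** The point holds in a limited form. A post-randomisation event that is part of the disease can determine membership of the primary efficacy population. The rule is left to the blinded review meeting, and the protocol's FAS check becomes optional and descriptive in the SAP. As the SAP stands, no guaranteed analysis would show whether selection had occurred.

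The likely size is modest: about 0.1 to 0.3 NRS points in either direction under the assumed vomiting rates, SD and correlation, and nil if vomiting is equally frequent on both treatments. The loss of pairs could matter more if whole subjects are dropped: at an assumed 10% rate, about 16 of 20 pairs would remain. The case rests on vomiting as a migraine symptom that effective treatment might change; the evidence for a direct drug effect is weak. This is worth correcting because the remedy is cheap. It does not by itself undermine the trial.

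**What to change.** 1. Reconcile the Protocol synopsis, 14.3.2 and 14.5 with SAP 9.2 and 11.8 on the role of vomiting in PP membership and on whether FAS efficacy results are mandatory.
2. In SAP 9.2 and 11.8, commit to fitting the MMRM of 11.8.1.3 to every dosed attack regardless of vomiting. Preferably this is the primary analysis; otherwise it is always reported beside the PP result.
3. Show exclusion for early post-dose vomiting as a sensitivity analysis at attack level, with its window fixed before the blind review.
4. Add to SAP 11.8.2 the number and percentage of subjects with at least one diary-recorded vomiting episode in the 24 hours after dosing, by treatment, with the paired difference of SAP 10.16.

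The cost is some wording, one further model run and one table, all from data already collected. The drawback is that the estimate on all dosed attacks includes some with incomplete absorption and may be slightly less favourable to the drug.

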14.3.3 Safety population

The safety population consists of all randomised subjects who receive at least one dose of IMP. The safety population will be used for the analysis of safety and tolerability data. Subjects will be analysed as treated, regardless of the randomised treatment assigned, if this differs from that to which the subject was randomised.

14.4 Subject disposition

The total number of subjects will be summarised. The duration on study, and number of subjects terminating the study treatment early, along with the reason for early study treatment termination will also be summarised.

14.5 Analysis of efficacy data

The primary population for analysis of efficacy data is the PP population. All summary tables and results of statistical analyses will be presented for the PP population for all efficacy endpoints. In addition, all

summary tables and results will be presented for the FAS population.

Individual pain score-time profiles for each treatment within each subject will be presented graphically. The difference between the NRS pain scores at each timepoint for LAT8881 60 mg compared with placebo within each subject will be estimated and presented graphically. The number of subjects, mean, standard deviation, minimum and maximum NRS pain score at each timepoint, change from baseline, difference between treatments at each timepoint and change from baseline difference between treatments will be presented for each treatment overall and within each treatment period.

Nausea, photophobia and phonophobia symptom scores will be summarised and presented in the same way as the pain scores. The number and percent of headaches with each most troublesome symptom of migraine including nausea, cognitive impairment, dizziness, functional disability, photophobia and phonophobia will be summarised for each treatment. The most troublesome symptom scores will be summarised and presented in the same way as the pain scores.

The number and percent of subjects with 'no headache pain' at each time point will be presented for each treatment. Two-way tables will present the presence/absence of pain classified for each treatment at each timepoint. Absence of pain will be defined as a pain NRS score of 0 or 1.

The number and percent of subjects who are "sustained pain-free" at 24 hours after dose of IMP will be presented by treatment. A two-way table will present the "sustained pain-free" status for subjects on each treatment.

The number and percent of subjects will be summarised by their first pain-free timepoint. A two-way table will present the classification of each subject's first pain-free timepoint by treatment. Kaplan-Meier curves will present the time to first pain-free timepoint.

Patient satisfaction for each treatment recorded on a 7-point Likert scale and the within-subject difference between treatments will be summarised. The mean difference between treatments will be compared with a paired t-test and the 95% confidence interval for the mean difference will be presented. Additional exploratory analyses to investigate the association between change in headache pain and symptom scores and selected subject baseline characteristics will be undertaken in a similar fashion with descriptive statistics.

